3.5.1.1 Best overall response and other binary endpoints

Best overall response

The Best overall response (BOR) is the best response recorded from the start of the treatment until disease progression/recurrence.

Only overall tumor assessments reported by investigator and performed before the start of any further anti-neoplastic therapies (i.e., any additional secondary anti-neoplastic therapy or surgery) will be considered in the assessment of best overall response.

Confirmation of complete and partial responses (CR and PR, respectively) must be made at least 4 weeks apart. Stable disease must occur > 6 weeks after the start of treatment.

Version 2.2

Confidential

Patients who are of unknown clinical response will be treated as non-responders.

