3.5.1.2 Computation of time to event endpoints

Overall survival

Overall survival (OS) is defined as the time from start of treatment to date of death due to any cause. If a patient is not known to have died, survival will be censored at the date of last contact.

As of protocol amendment 10, survival follow-up is no longer performed for patients who have discontinued study treatment in the Phase II part of the study.

Progression free survival

Progression-free survival (PFS) is defined as the time from the date of first study treatment intake to the date of the first documented disease progression or death due to any cause.

By default, if disease progression or death is documented after one single missing tumor evaluation, the actual event date of disease progression/death will be used for the PFS event date. If disease progression or death is documented after two or more missing tumor evaluations, the PFS time of these patients will be censored at the date of the last tumor evaluation with overall lesion response of CR, PR or SD. Patients who begin a new antineoplastic therapy prior to disease progression or death will be censored at the last adequate tumor evaluation prior to the start of the new antineoplastic therapy.

As of protocol amendment 10, post-treatment disease progression follow-up is no longer performed for patients who have discontinued study treatment in the Phase II part of the study.

Time to (overall) response

Time to (overall) response (TTR) will be based on "responders" only and is the time between the date of first treatment administration and the first documented response (CR or PR).

Duration of overall response

Duration of overall response (DOR) will be based on "responders" only and is the time between the date of first documented response (CR or PR) and the date of first documented progression or death due to underlying cancer. If progression or death due to underlying cancer has not occurred, then the patient is censored at the date of last adequate tumor assessment.

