3.5.3 Models and method of analysis

3.5.3.1 Analyses of time-to-event data

The following section presents the general methodology used to analyze time-to-event variables (e.g., PFS, OS, TTR and DOR) for Phase II efficacy assessments of tumor activity.

OS will be analyzed using Kaplan-Meier estimates with confidence intervals for median survival and survival probabilities for specific time-points (3, 6, 9, 12, 15, 18, 21, 24, 27, 30, 33, 36, 39, 42, 45, and 48 months).

PFS will be analyzed using Kaplan-Meier estimates (including plots) with 95% confidence interval for median survival and survival probabilities for specific time-points (3, 6, 9, 12, 15, 18, 21, 24, 27 and 30 months). PFS will be calculated at the MTD/RP2D for Phase II Arm 3 and Phase II Arm A. In addition, for the purposes of the PFS figure, PFS will be calculated for Phase Ib treatment arms as well.

Kaplan-Meier estimates based on all responders with 95% confidence intervals will be presented for TTR and DOR. These two analyses based on responders will be used as a descriptive analysis. Kaplan-Meier estimates with 95% confidence intervals for median TTR and median DOR will be presented. Survival probabilities for specific time-points will include 3, 6, 9, 12, 15 and 18 months for TTR and 3, 6, 9, 12, 15, 18, 21, 24, 27 and 30 months for DOR.

Details on Kaplan-Meier estimates

An estimate of the survival function can be constructed using the Kaplan-Meier (productlimit) method as implemented in PROC LIFETEST.

The median survival is obtained along with 95% confidence intervals as calculated from the PROC LIFETEST output (using method of [Brookmeyer & Crowley, 1982]).

Kaplan-Meier estimates with 95% confidence intervals at specific time points can be summarized. The confidence intervals are constructed using Greenwood's formula for the standard error of the Kaplan-Meier estimate. When the estimated survival function is close to zero or unity, symmetric intervals are inappropriate since they can lead to confidence limits that lie outside the interval [0, 1]. Any limit that is greater than unity will be replaced by 1.0. Any limit that is less than zero will be replaced by 0.0.

Hypotheses and test statistics

Not applicable.

Hazard ratio

Not applicable.

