3.5.3.2 Construction of waterfall graphs

The waterfall graph is used to depict anti-tumor activity. This plot displays both BOR and the best percentage change from baseline in the sum of diameter of all target lesions for each patient.

The assessments with an unknown overall response will **not be** excluded as long as the sum of diameter is correctly computed on the same lesions assessed at baseline.

The best overall response will be shown above each of the displayed bars in the graph.

Patients will be ordered in the graph using the following display (from left to right):

- Bars above the horizontal axis representing tumor growth
- Bars under the horizontal axis representing tumor shrinkage

Waterfall plots will show the cut-off limits for target lesions for PD (+20%) and PR (-30%) as dotted lines.

On the top of the waterfall plot a heatmap will be added in order to display per patient (matching with the bar on the waterfall plot) the information regarding BRAF local mutational status.

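### DOR has no censoring at new antineoplastic therapy or after missed evaluations, unlike PFS in the same subsection, so a responder's DOR can run past the date at which that patient's PFS is censored

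*SAP*

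**What the plan says.** Three response-based endpoints meet the same situation, a patient starting other anticancer treatment, and the SAP treats them differently.

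- **BOR (3.5.1.1).** Only investigator assessments "performed before the start of any further anti-neoplastic therapies" count. The parenthesis that follows includes surgery.
- **PFS (3.5.1.2).** "Patients who begin a new antineoplastic therapy prior to disease progression or death will be censored at the last adequate tumor evaluation" before that therapy starts. A second rule censors PFS at the last evaluation showing CR, PR or SD when the event is documented after two or more missing evaluations. Surgery is not named.
- **DOR (3.5.1.2).** The event is first documented progression or death due to the underlying cancer. Otherwise: "If progression or death due to underlying cancer has not occurred, then the patient is censored at the date of last adequate tumor assessment". Nothing is said about new therapy, surgery or missing evaluations, and there is no reference to the PFS rules.

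The same subsection adds a limit, for the Phase II part: "As of protocol amendment 10, post-treatment disease progression follow-up is no longer performed for patients who have discontinued study treatment".

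On reporting, 3.5.3.1 says "Kaplan-Meier estimates with 95% confidence intervals for median TTR and median DOR will be presented", with DOR probabilities out to 30 months. The final-CSR DOR tables are 14.2.5.1b (dual) and 14.2.5.1d (triple).

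For the waterfall, 3.5.3.2 says: "This plot displays both BOR and the best percentage change from baseline in the sum of diameter of all target lesions for each patient". The best percentage change is not restricted to scans before progression or before further therapy.

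**The concern.** DOR is a Phase II secondary endpoint (Table 1-1) meant to describe how long responses to the study combination last. If the clock keeps running after another treatment starts, part of the reported duration may belong to that treatment. In the same CSR, one responder could be censored in the PFS table and have an event many months later in the DOR table. A programmer who follows the DOR sentence literally and one who assumes it mirrors PFS will produce different tables, and the SAP does not say which is meant.

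The waterfall has a smaller form of the same gap. The BOR label above a bar stops at progression or further therapy, while the bar has no stated stop.

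**Working it through.** The SAP gives no figure to reproduce. The check is a comparison of the rules, two worked patients, and a simulation on assumed inputs.

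**1. Can the PFS rules be read into DOR?**

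| | New antineoplastic therapy | Surgery | Two or more missing evaluations | Death counted |
|---|---|---|---|---|
| BOR | assessments after it excluded | excluded too | no rule | not applicable |
| PFS | censored before it | not named | censored at last CR/PR/SD | any cause |
| DOR | no rule | no rule | no rule | underlying cancer only |

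No. DOR has its own event definition and its own censoring sentence, and the missing-evaluation rule is worded for PFS time only. The word adequate does not supply the cut either: the PFS sentence uses it and still has to spell out that the patient "will be censored at the last adequate tumor evaluation prior to the start of the new antineoplastic therapy". Sections 3.5.1.3 and 3.5.3.1 do not fill the gap.

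**2. Worked patients.** The dates are assumed and placed on the eight-weekly scan schedule of Table 2-1.

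*New therapy.* Response day 56, last scan before new therapy day 168, new therapy day 180, progression day 392.
- PFS: censored at day 168.
- DOR as written: event at 392 − 56 = 336 days.
- DOR under the PFS rule: censored at 168 − 56 = 112 days.

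*Missed scans.* Response day 56, scans to day 168, days 224 and 280 missed, progression day 336.
- PFS: censored at day 168.
- DOR as written: event at 336 − 56 = 280 days.
- DOR under the PFS rule: censored at 112 days.

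**3. Effect on median DOR.** All inputs here are assumptions. DOR on the combination is exponential with median 9 months.

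*(a) Switching unrelated to prognosis.* A share p of responders is given a switch time C, uniform over months 1 to 9; those with C before progression switch. With λ = ln 2 / 9 = 0.0770, the chance that C precedes progression is (e^(−0.0770) − e^(−0.693)) / (8 × 0.0770) = (0.926 − 0.500) / 0.616 = 0.69. For p = 0.20 to 0.30 this gives 14% to 21% of responders switching. After the switch, time to progression is exponential with the median shown. As written, the event falls at C plus that residual time; aligned, the patient is censored at C.

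| Residual median after switch | Median DOR as written | Aligned with PFS |
|---|---|---|
| 4.5 months | 8.2 to 8.4 | 9.0 |
| 9 months | 9.0 | 9.0 |
| 18 to 27 months | 9.5 to 10.1 | 9.0 |

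*(b) Switching ahead of progression.* For 10% to 30% of responders the switch falls uniformly between response and their own progression time, and the remaining time is multiplied by 1 to 3. Median DOR is 9.0 to 10.7 months as written and 9.6 to 11.3 months aligned. Here the aligned rule gives the longer median, because censoring at the switch is informative.

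**4. Can the aligned rule be programmed?** Yes. Section 2.1.2.10 imputes partial start dates of post-study therapies, and 3.3.2 identifies antineoplastic therapy given during or after study treatment.

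**The case against.** **Bias.** A reader might infer that the rule as written inflates median DOR. The documents do not support that. They give no switching rate and no outcome after switching, and the working above shows the shift can be positive, zero or negative. Where patients switch because progression is near, censoring at the switch is the more flattering rule. This objection stands.

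**Exposure.** Once amendment 10 applied, a Phase II patient who had stopped study treatment no longer had progression follow-up, so a late progression date on another therapy would not be collected. The new-therapy gap therefore matters only for scans collected before that amendment and for therapy given while still on study treatment. The SAP does not date the amendment, so the number affected cannot be derived. This stands too.

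**Waterfall.** A reader might infer that treatment beyond progression lets a bar and its label describe different treatments. It does not: that is continued study treatment (1.1), so it can make them cover different periods only. The one assessment rule in 3.5.3.2, that scans with unknown response are not "excluded as long as the sum of diameter is correctly computed on the same lesions assessed at baseline", may also limit the use of scans after a target lesion is resected. What remains is the absence of a stated cut at further therapy in a descriptive figure.

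**Estimand.** Following a response through later therapy can be a legitimate choice, and 3.5.3.1 calls the responder analyses descriptive, with no hypothesis test. But the SAP does not present DOR as such a choice, and it makes the opposite one for BOR and PFS. Section 3.5.1 refers to Protocol Appendix 14.1 for RECIST evaluation; that appendix was not available for this check. If it holds a DOR censoring rule, the SAP should cite it, because its own sentence now reads as complete.

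**Conclusion.** The inconsistency is real. DOR lacks both censoring rules that PFS has in the same subsection, and the pre-therapy restriction that BOR has. Followed literally, the DOR end date of a responder can fall after that patient's PFS censoring date and include time on a later treatment.

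For one patient the difference can be large: in both assumed examples a censored time of 112 days becomes an event, at 336 or 280 days. For the median it is modest and of unknown sign. Under the assumptions in 3(a) the as-written median differs from the aligned 9.0 months by between −0.8 and +1.1 months, and under 3(b) the aligned median is the larger one. The point rests on the text, not on these simulations. It does not touch the primary endpoints, DCR and ORR.

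**What to change.** In 3.5.1.2, state that DOR uses the same censoring rules as PFS: at the last adequate evaluation before a new antineoplastic therapy, and at the last evaluation with CR, PR or SD when the event follows two or more missing evaluations.

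Give one definition of further therapy, say in it whether surgery counts, and use it for BOR, PFS and DOR alike. Adding surgery to DOR alone would create a new mismatch, because the PFS sentence does not name it. While the paragraph is open, confirm that the different death events for PFS and DOR are intended.

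As a lesser change, in 3.5.3.2 take the best percentage change from the assessment window that defines the BOR label above each bar.

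The cost is SAP wording and one shared derivation, using therapy dates the plan already handles. Some DOR times will become shorter or censored, and censoring at a switch may be informative, as it already is for PFS. Reporting how many responders are censored for each reason would let readers judge that.

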3.5.1.3 Handling of missing data and special cases

No measurable lesion at baseline

Evaluation using RECIST criteria implies that patients have measurable lesion at baseline.

According to RECIST guidelines, the overall Response should be UNK or PD. In Phase I studies when the presence of target lesions is not mandatory for enrollment, in order to avoid the presence of too many "UNK" the overall response will be derived based on non-target lesions only when no target lesion is available. CR and SD will be assigned if the non-target lesion responses are respectively CR, non CR-non PD, respectively, without the appearance of a new lesion.

Analysis of other progression screening methods

In the efficacy analysis, additional screening methods (e.g., bone scans) are handled differently than the regular tumor assessments.

In addition, if the screening method is not available at a given assessment this does not automatically make the overall lesion response "Unknown" at that assessment.

Change in imaging modality

As per RECIST, the same imaging method used at baseline should also be used at all subsequent assessments. However, for various reasons such as site error (e.g., switch from MRI to CT) or renal dysfunction (making contrast a risk), this is not always done. The strict implementation of RECIST would mean that any change in the imaging method apart from that used at baseline would lead to an overall response of "unknown" at that assessment.

However, the presence or absence of contrast does not necessarily change the precision of the image. To cover that possibility, the following imaging modalities listed under the same bullet point below were considered the same for the calculation of change from baseline of the sum of diameters of target lesions (SOD):

- 'CT with contrast' and 'CT without contrast'
- 'Spiral CT with contrast' and 'Spiral CT without contrast'
- 'MRI with contrast', 'MRI without contrast', 'Dynamic contrast enhanced MRI' and 'Gadolinium-MRI'.

For other efficacy endpoints, investigator judgment only is considered even if overruling the computed response.

3.5.2 Non RECIST related endpoints

Not applicable.

3.5.3 Models and method of analysis

3.5.3.1 Analyses of time-to-event data

The following section presents the general methodology used to analyze time-to-event variables (e.g., PFS, OS, TTR and DOR) for Phase II efficacy assessments of tumor activity.

OS will be analyzed using Kaplan-Meier estimates with confidence intervals for median survival and survival probabilities for specific time-points (3, 6, 9, 12, 15, 18, 21, 24, 27, 30, 33, 36, 39, 42, 45, and 48 months).

PFS will be analyzed using Kaplan-Meier estimates (including plots) with 95% confidence interval for median survival and survival probabilities for specific time-points (3, 6, 9, 12, 15, 18, 21, 24, 27 and 30 months). PFS will be calculated at the MTD/RP2D for Phase II Arm 3 and Phase II Arm A. In addition, for the purposes of the PFS figure, PFS will be calculated for Phase Ib treatment arms as well.

Kaplan-Meier estimates based on all responders with 95% confidence intervals will be presented for TTR and DOR. These two analyses based on responders will be used as a descriptive analysis. Kaplan-Meier estimates with 95% confidence intervals for median TTR and median DOR will be presented. Survival probabilities for specific time-points will include 3, 6, 9, 12, 15 and 18 months for TTR and 3, 6, 9, 12, 15, 18, 21, 24, 27 and 30 months for DOR.

Details on Kaplan-Meier estimates

An estimate of the survival function can be constructed using the Kaplan-Meier (productlimit) method as implemented in PROC LIFETEST.

The median survival is obtained along with 95% confidence intervals as calculated from the PROC LIFETEST output (using method of [Brookmeyer & Crowley, 1982]).

Kaplan-Meier estimates with 95% confidence intervals at specific time points can be summarized. The confidence intervals are constructed using Greenwood's formula for the standard error of the Kaplan-Meier estimate. When the estimated survival function is close to zero or unity, symmetric intervals are inappropriate since they can lead to confidence limits that lie outside the interval [0, 1]. Any limit that is greater than unity will be replaced by 1.0. Any limit that is less than zero will be replaced by 0.0.

Hypotheses and test statistics

Not applicable.

Hazard ratio

Not applicable.

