An initial interim CSR will be prepared based on all Phase Ib/Phase II patient data from the dual study drug combination. The cut-off for reporting will be either LPFV + 18 months or when 80% of the patients can be assessed for progression free survival (PFS), whichever occurs first. Additional data for patients continuing to receive the MEK162 and LGX818 dual combination beyond the cutoff point for the initial reporting, as allowed by the protocol, and the Phase Ib/II data from the LGX818 and MEK162 and LEE011 triple combination will be summarized in a final CSR once all patients have discontinued the study. Although this SAP provides comprehensive detail on analyses performed throughout the lifetime of the study, only analyses included in the appendices for the final CSR (Section 4: Final Analysis Appendices) will be performed for the final analysis. For the presentation of results in the final analysis, LGX818, MEK162, and LEE011 will be referred to by their respective generic names: encorafenib, binimetinib, and ribociclib.

In this document, the dual and triple combination refers to the combination of LGX818 and MEK162, and LGX818 and MEK162 and LEE011, respectively, when not specified.

The purpose of the CSRs is to report the estimated maximum tolerated dose (MTD) and/or recommended phase II dose (RP2D), characterize the dose limiting toxicities (DLT), safety profile and efficacy of LGX818/MEK162 and LGX818/MEK162/LEE011 combinations in patients with solid tumors harboring a BRAF V600 mutation.

In addition, the CSR also report the assessment of clinical efficacy and safety of the LGX818 and MEK162 combination in patients with BRAF V600 mutant metastatic colorectal cancer (mCRC), patient with BRAF V600 mutant metastatic melanoma, who have progressed after prior selective BRAF inhibitor and patient with BRAF V600 mutant metastatic melanoma, who are naïve to prior selective BRAF inhibitor treatment.

[figure not shown]
An interim analysis is planned for the phase II part of patients with BRAF V600 mutant mCRC, when 50% of the total sample size (14 patients) have completed four cycles of treatment, to allow stopping early for futility when there is no treatment effect.

[figure not shown]
Note that obvious corrections will be made at the time of analysis to address minor formatting or spelling mistakes present in the SAP without the need to amend this document.

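### Landmark Kaplan-Meier intervals stay on the untransformed Greenwood scale with limits trimmed to 0 and 1, and no rule covers S(t) = 1 or 0, where the interval has zero width

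*SAP*

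**What the plan says.** SAP section 3.5.3.1, under the details on Kaplan-Meier estimates, provides for pointwise intervals ("Kaplan-Meier estimates with 95% confidence intervals at specific time points can be summarized") and names their basis: "The confidence intervals are constructed using Greenwood's formula for the standard error of the Kaplan-Meier estimate". It then warns that, for estimates close to zero or unity, "symmetric intervals are inappropriate since they can lead to confidence limits that lie outside the interval [0, 1". The only remedy is replacement: "Any limit that is greater than unity will be replaced by 1.0" and "Any limit that is less than zero will be replaced by 0.0". No transformation is named, and nothing is said about an estimate of exactly 1 or exactly 0.

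The same section sets the landmarks. OS has 16: "survival probabilities for specific time-points (3, 6, 9, 12, 15, 18, 21, 24, 27, 30, 33, 36, 39, 42, 45, and 48 months". PFS and DOR run in 3-month steps to 30 months, and TTR to 18 months. TTR and DOR use responders only: "Kaplan-Meier estimates based on all responders with 95% confidence intervals will be presented for TTR and DOR". Hypothesis tests and hazard ratios are marked as not applicable. Medians get a Brookmeyer-Crowley interval, which is a separate method.

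The only Phase II size in the SAP comes from the Introduction, which times the mCRC interim analysis "when 50% of the total sample size (14 patients) have completed four cycles of treatment". Section 2.3 adds that Arm 1 closed before reaching its planned number.

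**The concern.** The section identifies a weakness of symmetric limits near the boundary and then keeps them. A log-log interval cannot leave [0, 1], so the replacement rule has work to do only if the interval is untransformed. Cutting an upper limit of 1.03 back to 1.00 leaves the lower limit where it was, and that is the limit sitting too close to the estimate.

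The sharper problem is the case the section omits. Before the first event S(t) = 1, Greenwood's standard error is 0 and the interval is [1, 1], which claims certainty from a small sample. The opposite end is reached by construction for TTR. It is restricted to responders, so every patient analysed has the event, and S(t) is exactly 0 from the last response onwards. Any TTR landmark after that point has a zero or undefined standard error.

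What is at stake is reported precision in the Kaplan-Meier tables for the final report (Tables 14.2.2.1b/d, 14.2.3.1b/d, 14.2.4.1d and 14.2.5.1b/d). Elsewhere the SAP uses exact Clopper-Pearson limits for ORR and DCR. Without censoring, a landmark survival estimate is the same kind of proportion.

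**Working it through.** The SAP gives no figure to reproduce for these intervals, so the benchmark is the nominal 95%.

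**Inputs**
- Confidence level 95%, z = 1.960; Greenwood standard error; limits cut to [0, 1] (SAP 3.5.3.1).
- n = 14 / 0.50 = 28, the planned size of Arm 1 (SAP Introduction).
- n = 14 and n = 40 are assumptions to show the range. The SAP gives no size for Arms 2, 3 or A, nor the final size of Arm 1.

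**Formulas**, with no censoring before t and x of n patients event-free:
- Estimate S = x/n; Greenwood SE = sqrt(S(1 − S)/n).
- SAP interval: S ± 1.960 × SE, cut to [0, 1].
- Log-log interval: S^exp(±1.960 v), with v = sqrt((1 − S)/(nS)) / |ln S|.
- Exact lower limit when x = n: 0.025^(1/n).
- Coverage: the sum of Binomial(n, true S) probabilities over all x whose interval contains the true S.

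**One event in 28.** S = 27/28 = 0.964, SE = 0.0351. The raw interval is 0.896 to 1.033, reported as 0.896 to 1.000. Log-log (v = 1.00) gives 0.772 to 0.995.

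**No event in 28.** SE = 0, so the SAP interval is [1, 1]. The exact lower limit is 0.025^(1/28) = 0.877. At true S = 0.95 this outcome has probability 0.95^28 = 23.8%. For n = 14 the exact lower limit is 0.768 and the probability is 48.8%; for n = 40 they are 0.912 and 12.9%.

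**Coverage at n = 28**

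| True S | SAP interval | Log-log alone | Log-log, exact limit at S(t) = 0 or 1 |
|---|---|---|---|
| 0.50 | 91.3% | 93.9% | 93.9% |
| 0.80 | 92.4% | 95.9% | 95.9% |
| 0.90 | 94.3% | 89.3% | 94.5% |
| 0.95 | 76.0% | 71.3% | 95.1% |

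The last row in detail: at S = 0.95 the SAP interval contains the truth for x = 23 to 27, with probabilities 0.009 + 0.037 + 0.114 + 0.249 + 0.350, which give 0.760 before rounding. Almost all the loss is x = 28 (0.238). Log-log contains it for x = 25 to 27 (0.713); adding the exact limit at x = 28 gives 0.713 + 0.238 = 0.951.

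**Other sizes (assumed), SAP interval.** n = 14: 76.2% at S = 0.9 and 51.2% at S = 0.95. n = 40: 91.9%, 90.5%, 91.4% and 86.8% at S = 0.5, 0.8, 0.9 and 0.95. Coverage near 0 mirrors this: 76.0% at S = 0.05 for n = 28.

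**Effect of trimming.** The true S always lies in [0, 1], so cutting off the part outside cannot remove it. Trimmed and untrimmed limits have identical coverage.

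**Censoring check.** A simulation with 20% censored by t (8,000 runs per setting; estimates of exactly 0 or 1 counted as not covering) gives 48%, 73% and 84% for the SAP interval at S = 0.95 with n = 14, 28 and 40.

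**The case against.** The strongest reply is that the choice of scale matters little, and that the obvious alternative is no better where the problem is worst. Much of this stands. From S = 0.5 to 0.9 at n = 28 the SAP interval covers 91.3% to 94.7%, and at S = 0.6 it slightly beats log-log (94.7% against 93.9%). Log-log alone does worse than the SAP interval at S = 0.9 and S = 0.95. Once the no-event samples are set aside, the SAP interval at S = 0.95 covers 0.760 / 0.762 = 99.7%. The boundary failure is therefore a missing rule for zero standard error more than a matter of scale.

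Four stronger readings are tempting but unsupported:
- A reader might infer that trimming causes the under-coverage. It cannot, as shown above.
- A reader might infer that the SAP condemns its own method throughout. Its warning is limited to estimates close to zero or unity.
- A reader might infer that these intervals are the only inference in a trial without a comparator. ORR and DCR have exact intervals and the medians have Brookmeyer-Crowley intervals. The landmark values are secondary, and the SAP labels the TTR and DOR analyses descriptive.
- A reader might infer that most landmarks sit near a boundary. The SAP gives no expected survival figures to support that, apart from the certain arrival of TTR at 0.

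What survives is the untreated boundary and a modest mid-range shortfall, both cheap to repair.

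**Conclusion.** The point holds in this limited form. Section 3.5.3.1 keeps an interval it has just described as unsuitable near 0 and 1, treats only the visible overhang, and has no rule for an estimate of exactly 1 or 0. At n = 28 the cost is about 1 to 4 percentage points of coverage at S = 0.5, 0.8 and 0.9, and 19 points at S = 0.95, where roughly one sample in four would print [1, 1].

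The coverage figures assume no censoring before the landmark; 20% censoring lowers them slightly at S = 0.95. They rest on 28 as the planned size of Arm 1, which closed early; results for 14 and 40 patients are assumptions about unknown arm sizes. Responder-only analyses will have fewer patients than their arm. The consequence is overstated precision in descriptive tables. No trial decision is affected, and no defect is shown in the median intervals.

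**What to change.** In section 3.5.3.1:

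1. State that pointwise intervals for OS, PFS, TTR and DOR use the complementary log-log transform of the Kaplan-Meier estimate with Greenwood's variance (CONFTYPE=LOGLOG in PROC LIFETEST), and delete the two replacement sentences.
2. Add a boundary rule, without which step 1 is not a repair. Where S(t) = 1, show an exact binomial lower limit based on the number still at risk at t, which is conservative under censoring, or show 'NE'. Where S(t) = 0 nobody remains at risk, so show 'NE'. For TTR, where no responder is censored, an exact upper limit on the number of responders is also possible. Never print a zero-width interval.
3. Leave the Brookmeyer-Crowley interval for the median as it is.

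The cost is one procedure option, a short paragraph and a little programming for the boundary cells; no new data are needed. Intervals become asymmetric and wider on one side, and coverage falls slightly at some mid-range values (S = 0.6 above). If the interim report on the dual combination used the present rule, a footnote should explain why its landmark intervals differ from those in the final report.
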